2.2 Investigational product description

Among the different materials used as raw materials in dermal fillers, sodium hyaluronate, also denoted hyaluronic acid when found in vivo and hereinafter referred to as HA, is the most frequently used¹. Hyaluronic acid is a naturally occurring polysaccharide found in all vertebrates and in some bacteria^{1,2}. The chemical structure is very simple with repeating disaccharide units of glucuronic acid and N-acetylglucosamine. As the chemical structure of HA is identical in all species and tissues, it is non-allergenic.

To minimize the risk for contamination, the HA used in the manufacture of Galderma's HA gels is of non-animal source, biosynthesized from *Streptococcus* species of bacteria. During manufacturing, cross-links are introduced between the HA chains to obtain a gel network and as a result the duration of the gel in the body is several months, as compared to only a few

 GALDERMA	Title 43CH1508 Clinical Study Protocol	Doc id MA-29708
--	---	----------------------------------

Effective date: 2017-07-05 06:37

Effective

Version: 5.0

days for a solution of native HA. The HA gel is insoluble in water and organic solvents; however, the gel is highly hydrophilic and swells in water. Hyaluronic acid based fillers typically exhibit better biocompatibility and fewer adverse reactions than fillers based on other materials. The gel, when injected, acts by increasing the tissue volume, thereby improving tissue structure and support. The gel is gradually degraded over time and eventually the correction made will subside.

Restylane Defyne is a sterile, biodegradable, transparent gel of non-animal cross-linked HA containing a concentration of 20 mg HA per mL in a physiological buffer system. Lidocaine hydrochloride (3 mg/mL) is added to the formulation to diminish the pain resulting from the injection during the treatment. When the gel is injected and the tissue expands some pain can be experienced and it is therefore desirable to have a local anesthetic effect at the site of injection.

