瑞蓝 2 (Restylane) will degrade gradually in the body, typically 6-12 months after injection. With degradation the filler effect will disappear. The patients, who want to keep the filler effect, can receive follow-up injections when the filler effect becomes less visible or disappears.

The filler effect remains for longer than 6 months in the majority of patients as shown in the Chinese study, where patients were injected with 瑞蓝 2 (Restylane) in the nasolabial folds.

 GALDERMA	Title 43CH1508 Clinical Study Protocol	Doc id MA-29708
--	---	----------------------------------

Indications

瑞蓝 2 (Restylane) is intended to be used for facial tissue augmentation by injections into the mid dermis to correct moderate to severe nasolabial folds. 瑞蓝 2 (Restylane) should be injected into the middle part of the dermis layer of the facial skin. The injection procedure should strictly follow the rules of aseptic surgical technique. The product should only be used by doctors who have appropriate training, and experience, and who are knowledgeable about the anatomy at and around the site of injection.

Note! Injections of 瑞蓝 2 (Restylane) must only be done by plastic surgeons, dermatologists and cosmetic doctors at hospitals and medical plastic surgery institutions officially approved by the state administrative authorities. These institutions include clinics for medical cosmetic and plastic surgery, medical cosmetic outpatient departments and plastic surgery departments in general hospitals and specialized hospitals for medical cosmetic and plastic surgery, which must have obtained a "Medical Institution Business License". Doctors of those institutions should only use 瑞蓝2 (Restylane) after being trained and certified by the after sales service agent of the Swedish company Q-Med AB, Q-Med International Trading (Shanghai) Co., Ltd., and its appointed agents. After obtaining the training certificate, the doctors must strictly follow the instructions in this document (Instructions for Use).

Product Package and Traceability Information

The fill volume and number of needles in the package are stated on the carton of 瑞蓝 2 (Restylane). The package for 瑞蓝 2 (Restylane) with fill volume 0.5 mL/syringe contains one glass syringe with 0.5 mL 瑞蓝 2 (Restylane) gel and one needle. The package for 瑞蓝 2 (Restylane) with fill volume 1 mL/syringe contains one glass syringe with 1 mL 瑞蓝 2 (Restylane) gel and two needles. All needles are 30 G x ½" and sterilized by gamma irradiation.

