1.1.2 Number of subjects and randomization

Approximately 175 subjects will be enrolled and treated with Restylane Defyne in one NLF and Restylane in the opposite NLF, as randomly assigned to one of the two possible treatment sequences:

[figure not shown]
- Restylane Defyne in the subject's right NLF followed by Restylane in the subject's left NLF, or
- Restylane in the subject's right NLF followed by Restylane Defyne in the subject's left NLF.

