1.4 Efficacy Endpoints

1.4.1 Primary efficacy endpoint

The primary efficacy endpoint is the response rate based on the WSRS score, as assessed by the Blinded Evaluator at 6 months after last treatment.

Response rate is defined as the percentage of subjects with at least one (≥ 1) grade improvement on the WSRS.

 GALDERMA	Title SAP, 43CH1508, Restylane Defyne NLF	Doc id MA-31549
---	--	--------------------

Effective date:

2017-02-13 08:27

Effective

CCI

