2.4 Efficacy Analysis

2.4.1 *Data sets analyzed*

All efficacy variables will be analyzed using the FAS population. The primary analysis will be repeated using the PP population. If it is deemed necessary, other analyses will be repeated using the PP population.

2.4.2 *Handling of missing data*

As the study design is intra-individual, in which the outcome of both treatments to be compared is available on each subject, it is expected that when a data is missing, it will be missing for both NLFs in most of the cases. A majority of the deviations from the protocol can be expected to affect both NLFs and evaluations of the same subject the same way.

 GALDERMA	Title SAP, 43CH1508, Restylane Defyne NLF	Doc id MA-31549
--	--	----------------------------------

Effective date: 2017-02-13 08:27

Effective

Version: 1.0

FAS analyses of WSRS scores in the primary analysis will use multiple imputation method (MI) as the primary method for imputing missing values. Rather than imputing each missing observation by a single value, this approach represents a random sample of the missing values, and therefore accounts for the prediction uncertainty of the unknown missing values. Last observation carried forward (LOCF) will be used as an alternative imputation method.

Safety and PP analyses will be presented based on observed cases, i.e., no imputation of missing values will be performed.

(i) Use of MI

The imputation using MI will assume a Missing Completely at Random (MAR) mechanism. The MI procedure of the SAS® system will be used to generate five sets of data with missing values imputed from observed data. It is expected that the pattern of missing data will be monotonic, with slight deviations being corrected by the Markov Chain Monte Carlo (MCMC) method of the MI procedure. Linear regression will be employed to model the missing WSRS score, with the following covariates included in the imputation model: treatment and non-missing data from earlier time points (Baseline, Week 2, and Month 3). The imputed datasets will be analyzed using the methodology described for the primary analysis of response rates at Month 6. The results from the analysis of the multiple imputed datasets will be presented as appropriate. The seed number to be used will be 431508.

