2.4.3 Primary analysis

Non-inferiority testing of Restylane Defyne relative to Restylane will be assessed on the 95% confidence interval approach with a non-inferiority margin of 15%. The confidence interval will be constructed for the difference (Restylane minus Restylane Defyne) in response rates at the 6 months follow-up visit (Table 8-1 and Table 8-2). Non-inferiority will be declared if the two-sided 95% interval is fully below 15%, i.e., the upper bound of the interval is less than 15% in both the FAS and PP populations.

To assess the robustness of the results using the MI method, LOCF will be used as an alternative imputation method. The same summary of primary analysis results will also be presented for observed cases (OC), (Table 8-1).

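### LOCF, the planned robustness check on the imputed Month 6 result, is weak and usually non-conservative, and no planned analysis asks how much worse missing Restylane Defyne folds would have to be

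*SAP*

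**What the plan says.** SAP 2.4.2 makes multiple imputation (MI), labelled MAR, the primary method for missing WSRS scores in the full analysis set (FAS). It then adds: "Last observation carried forward (LOCF) will be used as an alternative imputation method". SAP 2.4.3 gives that alternative its purpose: "To assess the robustness of the results using the MI method, LOCF will be used as an alternative imputation method". The same section asks for the summary on observed cases. Table 8-1 prints the three rows together and labels LOCF and observed cases as sensitivity analyses. SAP 2.4.2 also expects that a missing score will, in most subjects, be missing for both folds.

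The endpoint in SAP 1.4.1 is a responder rate: "Response rate is defined as the percentage of subjects with at least one (≥ 1) grade improvement on the WSRS", taken at 6 months after last treatment. The decision rule in SAP 2.4.3 is: "Non-inferiority will be declared if the two-sided 95% interval is fully below 15" percent, for Restylane minus Restylane Defyne. The rule must be met in both the FAS, with MI, and the per-protocol (PP) set, which uses observed cases only.

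On the product, Protocol 2.2 says: "The gel is gradually degraded over time and eventually the correction made will subside". The Restylane instructions in Protocol Appendix 3 say: "With degradation the filler effect will disappear". They place degradation typically at 6 to 12 months and report that most patients in the Chinese study kept the effect beyond 6 months.

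**The concern.** LOCF treats an earlier score as the Month 6 score. The sources are Week 4, Month 3 or an early-termination visit, or baseline if nothing later exists. The method therefore assumes no waning between the last score and the primary time point, which sits badly with the stated behaviour of the gel.

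When both folds of a subject are carried forward with the same status, the subject adds a zero difference and no discordance. Both effects lower the upper bound. In a superiority trial that would usually be cautious; here it helps the claim.

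The other two rows do not fill the gap, because MI and observed cases both need missingness to be ignorable. If the three rows agree, the report may call the result robust without any analysis having asked what happens when the missing Restylane Defyne folds did worse than assumed.

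**Working it through.** **No plan figure to reproduce.** The sample-size sections of both documents are blacked out, and the visible text names no interval method for the paired difference. It gives no Week 4, Month 3 or Month 6 response rate.

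**Inputs from the documents.** About 175 subjects, each contributing both folds (SAP 1.1.2); margin 15 points and two-sided 95% interval (SAP 2.4.3).

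**Assumptions.** Discordance q = 20% of observed pairs; observed difference d (Restylane minus Restylane Defyne) from 0 to 10 points; both folds missing in 5%, 10% or 15% of subjects (9, 18 or 26). Observed cases stand in roughly for MI under MAR.

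**Formula.** Paired Wald upper bound: U = d + 1.96 × √((q − d²)/n).

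**1. Carried pairs concordant.** With missing fraction m, LOCF replaces d by (1 − m)d and q by (1 − m)q, and n returns to 175. For d = 9 points and 18 missing:
- Observed cases: 0.09 + 1.96 × √((0.20 − 0.0081)/157) = 0.159.
- LOCF: d = 0.09 × 157/175 = 0.0807 and q = 0.20 × 157/175 = 0.1794, so U = 0.0807 + 1.96 × √((0.1794 − 0.0065)/175) = 0.142.

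| d | Missing | U, observed cases | U, LOCF |
|---|---|---|---|
| 5 points | 18 | 12.0% | 10.7% |
| 9 points | 9 | 15.7% | 14.9% |
| 9 points | 18 | 15.9% | 14.2% |
| 10 points | 26 | 17.0% | 14.5% |

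In the last three rows LOCF passes where observed cases fail.

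**2. Dependence on waning.** If the carried difference is e, LOCF estimates (1 − m)d + m·e.
- Equal loss on both sides gives e = d, so the estimate is unbiased.
- Restylane Defyne wanes faster (e = 0 with 10% discordance among carried pairs, true d = 10 points, 26 missing): U is 16.5% with full data and 14.8% under LOCF.
- Restylane wanes faster (true d = −10 points, otherwise the same): U moves from −3.5% to −2.3%, against Restylane Defyne.

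**3. Carried scores that favour Restylane.** With e = 15 points, 25% discordance among carried pairs, d = 8 points and 18 missing, U is 14.9% on observed cases and 15.3% under LOCF. Here LOCF fails and observed cases pass.

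**4. What a departure from MAR would show.** Take d = 5 points and 18 missing pairs, of which j are scored Restylane responder and Restylane Defyne non-responder, the rest concordant.
- j = 6: U = 14.7%.
- j = 7: d = (0.05 × 157 + 7)/175 = 0.0849, q = (0.20 × 157 + 7)/175 = 0.2194, U = 15.3%. The result tips here.
- j = 18 (worst case): U = 22.3%.

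With d = 0, 14 of the 18 are needed. With d = 0 and only 9 missing, even the worst case gives 12.4%, so nothing can tip it.

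**5. A case at the margin.** Assume response of 92% against 90% at Month 3 and 80% against 65% at Month 6 (Restylane first), within-subject correlation 0.5, and last scores at Month 3. The LOCF difference is 0.95 × 15 + 0.05 × 2 = 14.35 points with 5% missing, 13.7 with 10% and 13.05 with 15%. In 40,000 simulated trials per setting, the LOCF row falls below 15% in about 5%, 7% and 10% of trials, against about 3.1% for observed cases.

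**The case against.** A reader might infer from step 5 that the chance of a false non-inferiority claim rises to 5–10%. The documents do not support that. LOCF decides nothing: the claim needs MI in the FAS and observed cases in the PP set. A rule that both must pass cannot pass more often than its PP component, about 3.1% in this scenario if FAS observed cases stand in for PP. The 5–10% figures are pass rates of a supporting row. Most of the excess would also be visible: about 4 of the 7 percentage points at 10% missing, and about 7 of the 10 at 15%, are trials in which the observed-case row of Table 8-1 fails.

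A reader might also infer that LOCF can never challenge the claim. Steps 2 and 3 show otherwise. A carried Week 4 score can be a non-response before touch-up, because touch-up is for folds not improved by at least one grade. An early-termination visit includes a blinded WSRS (Protocol 4.8.6) and can supply a score later than Month 3.

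The scenario in step 5 has Restylane Defyne losing 25 points and Restylane 12 between Months 3 and 6. No document supports faster waning of Restylane Defyne. Protocol 2.4.2 reports it clinically comparable to another filler up to Week 48, and Appendix 2 gives 69.8% still improved at 48 weeks. That carried scores are near their peak is likewise an inference: Appendix 3 places most of the degradation at 6 months or later.

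All of this stands, and it limits the size of the point. It does not supply the missing analysis. The observed-case rows also need ignorable missingness, and no delta-adjusted, tipping-point or worst-case analysis appears in the visible text.

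**Conclusion.** The point holds as a weakness in the sensitivity plan, worth correcting because the correction is cheap. LOCF is a weak check on MI. It is lenient when early scores agree or Restylane Defyne wanes faster, about neutral when both products wane equally, and able to move against Restylane Defyne otherwise. Nothing planned measures how far the missing Restylane Defyne folds could depart from MAR before non-inferiority is lost.

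The consequence is an unsupported statement of robustness; the trial's error rate is not shown to be inflated. Under 20% discordance and 10% missing, LOCF with concordant carried pairs lowers the bound by 1.3 points at d = 5 (12.0% to 10.7%) and 1.7 points at d = 9 (15.9% to 14.2%), while 7 of 18 unfavourable pairs would overturn a 5-point result. With 5% missing and no observed difference the issue has no practical effect. These sizes rest on assumed missingness, discordance and interval method, none of which the documents show.

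**What to change.** In SAP 2.4.2, 2.4.3 and Table 8-1, make a delta-adjusted (tipping-point) MI the robustness check:
- Impute Month 6 WSRS as planned.
- Worsen only the imputed Restylane Defyne scores, in pre-specified steps, and re-derive response.
- Report the upper 95% bound at each step and the shift at which it reaches 15%, or state that no shift in the range reaches it.

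Keep the observed-case row. Keep LOCF only as a descriptive row, without the robustness wording. Settle the base imputation model at the same time, since SAP 2.4.2 lists a Week 2 score as a covariate and the visit schedule has no Week 2 visit.

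The cost is SAP wording, a few extra SAS runs and one more table. The delta range must be fixed before database lock. The primary analysis, the visits and the data collected do not change.

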2.4.4 Subgroup analysis of primary endpoint

Graphical presentation, such as blobbogram, will be used to explore the differences in WSRS response rates between treatments by site, with corresponding 95% confidence intervals (Graph 8-1 and Graph 8-2).

[figure not shown]
 GALDERMA	Title SAP, 43CH1508, Restylane Defyne NLF	Doc id MA-31549
--	--	----------------------------------

Effective date: 2017-02-13 08:27

Effective

Version: 1.0

CCI

[figure not shown]

 GALDERMA	Title SAP, 43CH1508, Restylane Defyne NLF	Doc id MA-31549
--	---	---------------------------

2.5 Safety Analysis

All safety variables will be summarized descriptively based on the safety population.

CCI

2.5.2 *Adverse events*

All AEs will be coded according to MedDRA. Treatment emergent adverse events (TEAEs) will be summarized by System Organ Class (SOC) and Preferred Term (PT). The same summaries will be generated for treatment emergent related AEs, severe AEs, AEs leading to discontinuation, and serious AEs (SAEs). An overall summary of number and percentage of subjects with TEAEs reported in total, no TEAEs reported, related and unrelated TEAEs, and the number of events will be compiled (Table 9-5).

For related TEAEs, intensity of the AE will be summarized (Table 9-6). The number of days to onset (Table 9-8) and duration of event (Table 9-7) will be summarized by SOC and PT using number of events, mean, standard deviation, minimum, median, and maximum statistics. Action taken due to a related TEAE will be summarized by SOC, PT, and treatment (Table 9-9) using number of events.

Number and percentage of subjects with unrelated TEAEs and number of events will be presented by SOC, PT and intensity (Table 9-10).

Time to onset of a TEAE will be derived as the start date minus Day 1. If the start date is missing, it will be assumed that the AE started on Day 1.

Duration of a TEAE will be derived as the stop date minus the start date +1. If the start date is missing, it will be assumed that the AE started on Day 1. Missing stop date will not be imputed and therefore no duration will be calculated in these cases. Instead, the number of TEAEs that were ongoing at the end of the study will be given.

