4.8.2 Baseline Visit - Initial treatment (Day 1)

The baseline visit can be performed in direct connection with the screening visit or at the latest 21 days after the screening visit.

If the screening and baseline visits are separated, the inclusion and exclusion criteria will be re-checked and if any changes have occurred in the health status, concomitant medication and procedures will be assessed before the subject can be included in the study.

Further, vital signs will be assessed, standardized pre-treatment photograph will be taken as described in Section 7.5, and a pregnancy test (U-HCG) will be performed in women of childbearing potential. Before treatment, the blinded evaluator will make a live assessment to evaluate the wrinkle severity on WSRS to obtain a baseline value.

- Interview for medical history and concurrent diseases
- Interview for concomitant medications and treatments
- Vital signs (pulse rate, blood pressure, respiratory rate, and axillary temperature)

 GALDERMA	Title 43CH1508 Clinical Study Protocol	Doc id MA-29708
--	---	----------------------------------

Effective date: 2017-07-05 06:37

Effective date:

Effective

Version: 5.0

- Perform urine pregnancy test for all women of childbearing potential (if ≥ 2 weeks since the pregnancy test performed at the screening visit)
- Assess WSRS to obtain a baseline value (by blinded evaluator)
- Confirm eligibility criteria

[figure not shown]
For each eligible subject, one NLF will be randomly assigned to treatment with Restylane Defyne (with lidocaine) and the opposite NLF to treatment with Restylane (without lidocaine). Treatment will be administered according to the instructions in Section 6.6. Any device deficiencies or AEs since last visit, during or after the treatment will be reported. **CCI**

CCI

[figure not shown]
- Randomize the subject and arrange for blinding of the subject
- Obtain a pre-treatment photograph (baseline)
- Perform treatment in the right NLF according to randomization (Section 6.6)

CCI

- Perform treatment in the left NLF according to randomization (Section 6.6)

CCI

- Interview for AE since last visit and evaluate the subject for post-treatment AEs
- Evaluate device deficiencies

4.8.3 Week 4 follow-up after initial treatment (Day 29 ± 3 days) / Optional touch-up

A follow-up visit will take place 4 weeks ($D29 \pm 3$ days) after the initial treatment. An optional touch-up treatment may be performed if optimal aesthetic improvement was not obtained.

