8.4.8 Anticipated adverse events

After the injection some common injection-related reactions might occur with both products. These reactions include bruising, erythema, swelling, pain, tenderness and itching at the injections site. Typically these reactions start on the day of treatment and resolve spontaneous within a few days after injection. This is in line with what has been observed in the Chinese clinical study for Restylane and is also consistent with international clinical study results for Restylane and Restylane Defyne.

Refer to the Restylane Defyne IB and EU IFU ([Appendix 2](#)) as well as the Restylane China IFU ([Appendix 3](#)).

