10.5 Safety analysis

CCI

All AEs will be coded according to MedDRA. All adverse events will be summarized by system organ class (SOC) and preferred term (PT). The same summaries will be generated for related AEs, severe AEs, AEs leading to discontinuation, and SAEs. For related AEs, the number of days to onset and the duration of event will be summarized by SOC and PT using mean, SD, min, max, and median statistics.

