Injection related adverse events such as bruising, erythema, itching, swelling, pain and tenderness generally resolve spontaneously within one week after injection.

Vascular compromise may occur due to an inadvertent intravascular injection or as a result of vascular compression associated with implantation of any injectable product. This may manifest as ischemia or necrosis at the implant site or in the area supplied by the blood

 GALDERMA	Title 43CH1508 Clinical Study Protocol	Doc id MA-29708
--	---	----------------------------------

Effective date: 2017-07-05 06:37

Effective

Version: 5.0

vessels affected; or rarely as ischemic events in other organs due to embolisation. Following facial aesthetic treatments isolated rare cases have been reported regarding ischemic events affecting the eye leading to visual loss, and the brain resulting in cerebral infarction. After injections of the nose ischemia/necrosis may occur, especially in patients who had prior rhinoplasty.

Symptoms of inflammation at the implant site commencing either shortly after injection or after a delay of up to several weeks have been reported. In case of unexplained inflammatory reactions infections should be excluded and treated if necessary since inadequately treated infections may progress into complications such as abscess formation. Treatment using only oral corticosteroids without concurrent antibiotic treatment is not recommended. In case of persistent or recurrent inflammatory symptoms, consider removal of the product by aspiration/drainage, extrusion or enzymatic degradation (use of hyaluronidase has been described in scientific publications). Before any removal procedure is performed, the swelling may be reduced by using e.g., NSAID for 2-7 days or a short course of corticosteroids for less than 7 days, in order to more easily palpate any remaining product.

For patients who have experienced medically important adverse events, a decision for retreatment should take into consideration the cause and severity of previous reactions.

For reporting adverse events contact your local Galderma representative or distributor for this product.

IX. PERFORMANCE

In a randomized controlled multicenter study with Restylane Defyne for correction of moderate to severe nasolabial folds, 69.8% of subjects maintained a clinically significant improvement at 48 weeks after treatment.

X. TREATMENT PROCEDURE

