1.6 Safety Endpoints

Safety endpoints include:

- (i) **Incidence, intensity, duration and time to onset of related treatment emergent AEs collected during the whole study**

CCI

2 Statistical Methods

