9.3.2 Related TEAEs

Table 9-6: Related TEAEs by MedDRA System Organ Class, Preferred Term, and intensity, Safety population

Primary System Organ Class Preferred Term	Restylane Defyne									Restylane									Total					
	Events	Subjects	Intensity						Events	Subjects	Intensity						Events	Subjects						
			Mild		Moderate		Severe				Mild		Moderate		Severe									
	n	n	%	n	%	n	%	n	%	n	n	%	n	%	n	%	n	n	%	n	%			
SOC																								
PT																								
PT																								
...																								
SOC																								
PT																								
PT																								
...																								
All¹⁾																								

% = n / number of subjects in Safety population (N = xxx) * 100

1) A single subject may have reported several related TEAEs.

 GALDERMA	Title SAP, 43CH1508, Restylane Defyne NLF	Doc id MA-31549
--	--	--------------------

Table 9-7: Duration (number of days days) of related TEAEs by MedDRA System Organ Class and Preferred Term, Safety population

Primary System Organ Class Preferred Term	Restylane Defyne						Restylane					
	Events n	Mean	SD	Min	Median	Max	n	Mean	SD	Min	Median	Max
SOC												
PT												
PT												
...												
SOC												
PT												
PT												
...												
All												

If applicable, list TEAEs ongoing at study end here, alternatively create a summary table.

 GALDERMA	Title SAP, 43CH1508, Restylane Defyne NLF	Doc id MA-31549
--	--	--------------------

Table 9-8: Time to onset (number of days) from treatment for related TEAEs by MedDRA System Organ Class and Preferred Term, Safety population

Primary System Organ Class Preferred Term	Restylane Defyne						Restylane					
	Events n	Mean	SD	Min	Median	Max	n	Mean	SD	Min	Median	Max
SOC												
PT												
PT												
...												
SOC												
PT												
PT												
...												
All												

Any extra comments here...

 GALDERMA	Title SAP, 43CH1508, Restylane Defyne NLF	Doc id MA-31549
--	--	--------------------

Table 9-9: Action taken due to related TEAEs by MedDRA System Organ Class and Preferred Term, Safety population

Primary System Organ Class Preferred Term	Action Taken							
	Restylane Defyne				Restylane			
	None	Medication treatment	Non-pharmacological treatment or other procedures/tests	Subject withdrawn	None	Medication treatment	Non-pharmacological treatment or other procedures/tests	Subject withdrawn
SOC								

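### Time to onset is counted from Day 1 even after touch-up, so a reaction on the day of the second injection is tabulated at 28 days (25–31)

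*SAP*

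**What the plan says.** Safety endpoint (i) in SAP 1.6 is "Incidence, intensity, duration and time to onset of related treatment emergent AEs collected during the whole study". SAP 2.5.2 gives the derivation: "Time to onset of a TEAE will be derived as the start date minus Day 1". For missing dates it adds "If the start date is missing, it will be assumed that the AE started on Day 1", and applies this to both onset and duration. Duration is stop date minus start date plus 1. A missing stop date is not imputed, and no duration is then calculated.

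The results go into Table 9-8 (SAP 9.3.2), titled "Time to onset (number of days) from treatment for related TEAEs", and Table 9-7 (duration). Both have one set of columns per product and no split by treatment session.

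The protocol has two possible sessions. Day 1 is the initial treatment. At the Week 4 visit (Day 29 ± 3, Protocol 4.8.3), "An optional touch-up treatment may be performed if optimal aesthetic improvement was not obtained", and adverse events connected with that injection are recorded. Protocol 10.5 says only that "the number of days to onset and the duration of event will be summarized by SOC and PT", without naming a reference date.

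**The concern.** For an event after touch-up, the derivation in SAP 2.5.2 and the title of Table 9-8 point to different dates. The title suggests time since treatment. The rule gives time since the first treatment, whichever injection preceded the event.

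This matters because onset separates two clinical patterns that the documents themselves describe. Protocol 8.4.8 says of injection reactions: "Typically these reactions start on the day of treatment and resolve spontaneous within a few days after injection". The Restylane Defyne instructions for use (Protocol Appendix 2) also state: "Symptoms of inflammation at the implant site commencing either shortly after injection or after a delay of up to several weeks have been reported". A same-day reaction to the touch-up, tabulated at about four weeks, looks like the second pattern.

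The missing-date default is a separate problem and affects different events. It places the start of a touch-up event before the touch-up injection and so lengthens its duration.

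**Working it through.** The documents state no onset figure to reproduce, so the check applies their own date rules.

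**Inputs.** Onset = start day − 1, and duration = stop day − start day + 1 (SAP 2.5.2). Touch-up falls on Day 29, window Day 26 to Day 32 (Protocol 4.8.3).

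**Onset of a reaction starting on the touch-up day.** 29 − 1 = 28 days; across the window, 26 − 1 = 25 to 32 − 1 = 31. Counted from the touch-up it is 0.

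**Effect on Table 9-8 (assumed rates).** Let f be the fraction of subjects touched up and r the number of events per touch-up relative to the initial session. The documents give neither. Suppose every reaction starts on its injection day, so the true mean and SD are 0. The share of events after touch-up is p = f·r/(1 + f·r), the tabulated mean is 28p and the SD is 28·√(p(1 − p)).

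| r | f | p | Mean (days) | SD (days) |
|---|---|---|---|---|
| 1 | 10% | 0.091 | 2.55 | 8.05 |
| 1 | 20% | 0.167 | 4.67 | 10.43 |
| 1 | 30% | 0.231 | 6.46 | 11.80 |
| 1/3 | 10% | 0.032 | 0.90 | 4.95 |
| 1/3 | 20% | 0.0625 | 1.75 | 6.78 |
| 1/3 | 30% | 0.091 | 2.55 | 8.05 |

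The value r = 1/3 equals the ratio of the recommended maximum volumes, 0.5 mL to 1.5 mL.

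**With a genuine late event.** An all-zero truth exaggerates the contrast. Take 175 initial and 35 touch-up events, one of the initial ones starting 90 days after Day 1.
- True values: 209 zeros and one 90, giving mean 0.43, SD 6.20, maximum 90.
- Tabulated values: 174 zeros, one 90 and 35 at 28, giving mean (90 + 35 × 28)/210 = 5.10, SD 11.97, maximum 90.

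The mean and SD still move; the maximum does not.

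**Comparison of products (20% touched up, one event per injected fold).** If all 35 touch-ups are bilateral, both products show 28 × 35/210 = 4.67, a difference of 0. If 10 of the 35 treat one fold only, always with the same product, the other product shows 28 × 25/200 = 3.50, a difference of 1.17 days.

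**Median.** It leaves 0 only when at least half the events in a row follow touch-up. With p = 1/6 and independent events:
- two-event row: 1 − (5/6)² = 0.306;
- five-event row: P(at least 3 of 5) = 0.035.

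**Missing start date, stop date known.**
- A 5-day event from Day 29 to Day 33 gets duration 33 − 1 + 1 = 33 (30 for a Day 26 touch-up, 36 for Day 32) and onset 0. That onset is right only by coincidence.
- A 5-day event starting 14 days after touch-up (Day 43 to Day 47) gets duration 47 (44–50) and onset 0, where 14 from touch-up is true.

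**The case against.** The strongest reply is that the SAP states its anchor openly and that counting from first exposure is a legitimate convention. On that reading the Table 9-8 title is loose rather than contradictory, and Protocol 10.5 is not breached because it names no date. Re-anchoring also has a cost: a delayed reaction to the first injection that starts on Day 30 is 29 days from Day 1 but only 1 day from a Day 29 touch-up. This stands as an argument for showing both figures. It does not rescue an unsplit table that mixes the two sessions under an ambiguous title.

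The size is assumed. Touch-up is optional, needs consent, is limited to subjects with less than one grade of improvement in at least one fold, and is barred during ongoing treatment-related events. It is preferably bilateral, which shifts both products alike. Equal event rates per session may be an upper case. All of this stands and keeps the point minor.

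On duration, the effect needs a missing start date together with a known stop date. Start date is a listed eCRF item (Protocol 8.4.3), so cases are probably few. The default is also generic: it would lengthen any late event with a missing start date, touched up or not. That is true, and is a further reason to change it.

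Table 7-12 does show directly observed events by session, but only as yes/no counts without onset days. Adjacent safety text is redacted and could contain a session split. The adverse event rules in 2.5.2 and the shells of Tables 9-7 and 9-8 are visible and contain none.

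**Conclusion.** The concern holds, as a minor point. The 28 days (25–31) for a same-day touch-up reaction follows from the documents with no assumption, and nothing visible re-anchors it. The effect on the mean and SD of Table 9-8 depends on unstated touch-up and event rates and on most reactions being same-day. A distorted product comparison further needs one-sided touch-up or unequal touch-up event rates. The duration error is certain for a touch-up event with a missing start and a recorded stop date, but is probably rare.

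Events before touch-up with complete dates are derived correctly. The primary non-inferiority analysis and the incidence and intensity of adverse events are unaffected. What is affected is the onset and duration part of a named safety endpoint, reported descriptively.

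**What to change.** In SAP 2.5.2:

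- Derive onset from the most recent injection of the affected fold on or before the start date, or of either fold if the event cannot be attributed to one.
- Present Table 9-8 separately for events starting before touch-up (or with no touch-up) and after touch-up.
- For post-touch-up events, also show days from Day 1, labelled as from initial treatment, so that a delayed reaction to the first injection is not hidden. The bar on touch-up during ongoing treatment-related events confines this ambiguity to events that begin after touch-up.
- Replace the Day 1 default. Set a missing start date to the later of the most recent injection before the event was first recorded and the previous adverse event interview, consistent with any partial date and not after the stop date.

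If Day 1 is kept as the only anchor, at least retitle Table 9-8 as days from initial treatment and split it by session.

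The cost is a few lines of SAP text, one split and one added set of rows in the Table 9-8 shell, and a little programming. Injection dates for both sessions (Protocol 6.6.5) and event start dates (Protocol 8.4.3) are already recorded. The one drawback is that post-touch-up events carry two onset figures.
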